6.3 Patient numbering, treatment assignment, randomization

6.3.1 Patient numbering

Each patient is identified in the study by a Patient Number (Patient No.), that is assigned when the patient is first enrolled for screening and is retained as the primary identifier for the subject throughout his/her entire participation in the trial. The Patient No. consists of the Center Number (Center No.) (as assigned by Novartis to the investigative site) with a sequential patient number suffixed to it, so that each patient is numbered uniquely across the entire database. Upon signing the informed consent form, the patient is assigned to the next sequential Patient No. available.

6.3.2 Treatment assignment, randomization

Patients will be randomized to one of the two treatment arms in a ratio of 1:1.

The randomization numbers will be generated using the following procedure to ensure that treatment assignment is unbiased. A randomization list will be produced by or under the responsibility of the Novartis Nürnberg GCP Officer using a validated system that automates the random assignment of treatment arms to randomization numbers in the specified ratio.

The randomization scheme will be reviewed by a Biostatistics Quality Assurance Group and locked by them after approval.

Prior to dosing, all patients who fulfill all inclusion/exclusion criteria will be randomized to one of the treatment arms according to the randomization scheme.

6.4 Treatment blinding

Treatment will be open label to subjects, investigator staff, persons performing the assessments, and the clinical trial team.

6.5 Dose escalation and dose modification

6.5.1 Dose escalation guidelines

Dose escalation will be allowed from 50 mg QD to 75 mg QD for eltrombopag as described in Section 6.1. Patients will be treated with eltrombopag 50 mg QD for 2 weeks to reach a target platelet count of \geq 50 × 10⁹/L. For those patients who do not achieve the target platelet count within 2 weeks, the dose of eltrombopag will be increased to 75 mg QD.

Patients who will have platelet $< 30 \times 10^{9}$ /L after 3 cycles with dexamethasone, treatment with eltrombopag will be initiated at 50 mg/day till Week 52 with eltrombopag dose adjustments summarized in Table 6-4.

All escalations and de-escalations must be recorded on the Dosage Administration Record eCRF.

6.5.1.1 Starting dose

In this study, the starting dose will be 50 mg eltrombopag QD (starting dose for Asian patients will be 25 mg QD, reduced as per Section 6.1.1).

This eltrombopag starting dose is consistent with the dosing guidelines that have been approved for eltrombopag use in adult patients with chronic ITP.

6.5.2 Dose modifications

For patients who do not tolerate the protocol-specified dosing schedule, dose interruptions and/or reductions are either recommended or mandated in order to allow patients to continue the study treatment.

These dose modifications are summarized in Table 6-4. Deviations to mandatory dose interruptions and/or reductions are not allowed. Permanent treatment discontinuation is mandatory for specific events indicated as such in Table 6-5.

Dose adjustment or response
Increase daily dose by 25 mg to a maximum of 75 mg/day
Decrease daily dose by 25 mg. Wait 2 weeks to assess the effects of this and any subsequent dose adjustments ^a
Stop eltrombopag; increase the frequency of platelet monitoring to twice weekly. Once the platelet count is < 150 × 10 ⁹ /L, reinitiate therapy at a lower dose

Table 6-4Eltrombopag Dose Adjustments in ITP

These dose changes must be recorded on the appropriate CRF.

Eltrombopag can cause hepatobiliary laboratory abnormalities, severe hepatotoxicity, and potentially fatal liver injury. Serum ALT, AST and bilirubin should be measured prior to initiation of eltrombopag, every 2 weeks during the dose adjustment phase and monthly after establishment of a stable dose. Abnormal serum liver tests should be evaluated with repeat testing within 3 to 5 days. If the abnormalities are confirmed, serum liver tests should be monitored weekly until the abnormalities resolve, stabilize, or return to baseline levels.

For the grading of AEs and laboratory results, the Common Terminology Criteria for Adverse Events (CTCAE) Version 5.0 will be used.

Please refer to the label for dexamethasone for guidance of dose adjustments.

Table 6-5Criteria for dose adjustment based on liver enzyme and bilirubin
levels

	Dose modifications for Eltrombopag
Worst toxicity CTCAE ^a Grade (value) during the treatment	Investigations (Hepatic)
Isolated Total Bilirubi	n Elevation
> ULN – 1.5 × ULN	Maintain dose level
> 1.5 - 3.0 × ULN*	Interrupt dosing and weekly monitor liver function tests (LFTs) ^b , or more frequently if clinically indicated, until resolved to \leq 1.5 × ULN:
	If resolved in \leq 14 days, then resume at same dose level
	If resolved in > 14 days, then decrease one dose level ^e
> 3.0 - 10.0 × ULN**	Mandatory: Interrupt dosing and weekly monitor LFTs ^b , or more frequently if clinically indicated, until resolved to $\leq 1.5 \times ULN$:
	If resolved in \leq 14 days, then decrease one dose level ^e If resolved in > 14 days, then discontinue patient from study drug treatment. LFTs ^b will continue to be monitored weekly, or more frequently if clinically indicated, until total bilirubin have resolved to baseline or stabilization over 4 weeks.

	Dose modifications for Eltrombopag
Worst toxicity CTCAE ^a Grade (value) during the treatment	Investigations (Hepatic)
> 10.0 × ULN	Mandatory: Discontinue patient from study drug treatment
	The patient should be monitored weekly (including LFTs ^b), or more frequently if clinically indicated, until total bilirubin have resolved to baseline or stabilization over 4 weeks.
	 * Note: If total bilirubin > 1.5 - ≤ 3 x ULN is due to the indirect (non-conjugated) component only, no changes to dose are required. ** Note: If total bilirubin > 3.0 - 10.0 x ULN is due to the indirect (non-conjugated) component only, and hemolysis as the etiology has been ruled out as per institutional guidelines (e.g., review of peripheral blood smear and haptoglobin determination), then decrease 1 dose level^e and continue treatment at the discretion of the investigator
Isolated AST or ALT e	levation
> ULN - 3.0 × ULN	Maintain dose level
> 3.0 - 5.0 × ULN	Maintain dose level. Repeat LFTs ^b as soon as possible, preferably within 48-72 hours from awareness of the abnormal results. If abnormal lab values are confirmed upon the repeat test, then monitor LFTs ^b weekly, or more frequently if clinically indicated, until resolved to \leq 3.0 × ULN
	Discontinue patient from the study drug treatment if elevation is combined with any o the following: Clinical symptoms of liver injury or evidence for hepatic decompensation Progressively increasing LFTs ^b upon repeat testing Persistence ≥4 weeks
> 5.0 - 10.0 × ULN	Mandatory: Interrupt dose.
	Repeat LFTs ^b as soon as possible; preferably within 48-72 hours from awareness of the abnormal results. Monitor LFTs ^b weekly, or more frequently if clinically indicated until resolved to \leq 3.0 x ULN then:
	If resolved in ≤14 days, maintain dose level
	If resolved >14 days, decrease one dose level ^e
> 10.0 - 20.0 × ULN	Mandatory: Interrupt dose.
	Repeat LFTs ^b as soon as possible, preferably within 48-72 hours from awareness of the abnormal results. Monitor LFTs ^b weekly, or more frequently if clinically indicated until resolved to ≤ baseline. Then decrease one dose level ^e
> 20.0 × ULN	Mandatory: Discontinue patient from study drug treatment Repeat LFTs ^b as soon as possible, preferably within 48-72 hours from awareness of the abnormal results. Monitor LFTs ^b weekly, or more frequently if clinically indicated until resolved to ≤ baseline or stabilization over 4 weeks.

	Dose modifications for Eltrombopag
Worst toxicity CTCAE ^a Grade (value) during the treatment	Investigations (Hepatic)
For patients with normal baseline ALT and AST and total bilirubin value [AST or ALT > 3.0 × ULN] combined with [total bilirubin > 2.0 × ULN] without evidence of cholestasis ^d OR For patients with elevated baseline AST or ALT [AST or ALT > 3 × baseline] OR [AST or ALT > 5.0 × ULN], whichever is lower, combined with [total bilirubin > 2× baseline	Mandatory: Permanently discontinue patients from study drug treatment. Repeat as soon as possible, preferably within 48 hours from awareness of the abnormal results, then with weekly monitoring of LFTs ^b), or more frequently if clinically indicated, until AST, ALT, or bilirubin have resolved to baseline or stabilization over 4 weeks
^a Common Toxicity Criter ^b Core LFTs consist of A ULN), and alkaline phosp ^c "Combined" defined as the defined threshold If combined elevations or instructions for isolated e	iould be based on the worst preceding toxicity. ria for Adverse Events (CTCAE Version 5.0) LT, AST, GGT, total bilirubin (fractionated [direct and indirect], if total bilirubin > 2.0 x obtatase (fractionated [quantification of isoforms], if alkaline phosphatase > 2.0 x ULN. total bilirubin increase to the defined threshold concurrently with ALT/AST increase to f AST or ALT and total bilirubin do not meet the defined thresholds, please follow the elevation of total bilirubin and isolated elevation of AST/ALT, and take a conservative ree of the elevations (e.g. discontinue treatment at the situation when omit dose is

needed for one parameter and discontinue treatment is required for another parameter). After all elevations resolve to the defined thresholds that allow treatment re-initiation, re-start the treatment either at the same dose or at one dose lower if meeting a criterion for dose reduction

^d "Cholestasis" defined as alkaline phosphatase (ALP) elevation (>2.0 x ULN and R value <2) in patients without bone metastasis, or elevation of ALP liver fraction in patients with bone metastasis

The R value is calculated by dividing the ALT by the ALP, using multiples of the ULN for both values. It denotes whether the relative pattern of ALT and/or ALP elevation is due to cholestatic ($R \le 2$), hepatocellular ($R \ge 5$), or mixed (R > 2 and < 5) liver injury.

^e "One dose level" defined as eltrombopag dose reduction by 25 mg.

6.5.3 Follow-up for toxicities

Patients whose treatment is interrupted or permanently discontinued due to an AE or clinically significant laboratory value, must be followed up at least once a week (or more frequently if required by institutional practices, or if clinically indicated) for 4 weeks, and subsequently at approximately at least 4-week intervals (or more frequently if required by institutional practices, or if clinically indicated), until resolution or stabilization of the event, whichever comes first. Appropriate clinical experts such as ophthalmologist, etc. should be consulted as deemed necessary.

Patients who permanently discontinue eltrombopag for an AE or clinically significant laboratory value will be discontinued from the study and then undergo a 30-day safety follow-up.

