Platelet counts above the normal range present a theoretical risk for thrombotic/thromboembolic complications. In eltrombopag clinical trials thromboembolic events were observed at low and normal platelet counts. Caution must be used when administering eltrombopag to patients with known risk factors for thromboembolism including but not limited to inherited (e.g., Factor V Leiden) or acquired risk factors (e.g., ATIII deficiency, antiphospholipid syndrome), patients with prolonged periods of immobilization, malignancies, contraceptives and hormone replacement therapy, surgery/trauma, obesity and smoking. Platelet counts must be closely monitored and dose modifications must be made in accordance with parameters provided in the protocol. The risks of thromboembolism and any of the following complications versus the benefit of improved platelet counts must be evaluated by the Investigator for each patient with known risks of thromboembolic events.

Cataracts:

Cataracts were observed in toxicology studies of eltrombopag in rodents. The data from the double-blind and open label ITP and HORT studies, as well as data from the LENS study and the Phase II HCV study did not suggest an increased risk of cataract development in subjects treated with eltrombopag. This conclusion was supported by the blinded, independent ocular safety data review from the Clinical Events Committee (CEC). In the pooled data from the Phase III HCV studies (ENABLE studies), where subjects received up to 57 weeks of eltrombopag at doses up to 100 mg, there was a numerically higher incidence of cataracts in the eltrombopag treatment group compared with the placebo group. Routine monitoring of patients for cataracts is recommended.

Bleeding following discontinuation of eltrombopag

Thrombocytopenia is likely to reoccur in ITP patients upon discontinuation of treatment with eltrombopag. Following discontinuation of eltrombopag, platelet counts return to baseline levels within 2 weeks in the majority of patients, which increases the bleeding risk and in some cases may lead to bleeding. This risk is increased if eltrombopag treatment is discontinued in the presence of anticoagulants or anti-platelet agents.

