6.1 Study treatment

Patients randomized to Arm A will receive eltrombopag in combination with a short course of high-dose dexamethasone beginning at Day 1. The dose of dexamethasone will be 40 mg QD for 4 consecutive days and limited to 1 cycle. The starting dose of eltrombopag will be 50 mg QD and treatment will continue at the same dose for 2 weeks to reach a target platelet count of 50×10^{9} /L as necessary to reduce the risk for bleeding. The dose of eltrombopag will be increased by 25 mg increments every 2 weeks to a maximum dose of 75 mg QD for all patients who do not achieve the target platelet count of $> 50 \times 10^{9}$ /L (Table 6-1). Treatment with eltrombopag will be continued at the minimal dosage necessary to maintain a platelet count \geq 50 × 10⁹/L to 150 × 10⁹/L for 20 weeks. Asian patients will initially receive half of the dose, starting at 25 mg of eltrombopag due to lower clearance of eltrombopag as compared with non-asian patients. After initiating eltrombopag, the dose must be adjusted to achieve and maintain a platelet count $> 50 \times 10^9$ /L as necessary to reduce the risk for bleeding. The standard eltrombopag dose adjustment for Asian patients would be 25 mg once daily as well. It is necessary to wait for at least 2 weeks to see the effect of any dose adjustment on the patient's platelet response prior to considering another dose adjustment. A daily dose of 75 mg must not be exceeded. The dose of eltrombopag will be decreased by 25 mg if platelet counts are $> 150 \times 10^{9}$ /L to $\leq 400 \times 10^{9}$ /L by 25 mg and the effect will be assessed after 2 weeks.

Patients will be eligible for taper off and treatment discontinuation once they reach platelet counts $\ge 30 \times 10^9$ /L. The duration of tapering will be 6 weeks starting at W21D1: decrease in dose will be performed by 25 mg reductions every 2 weeks to a minimum dose of 25 mg every other day for all patients.

Table 6-1Eltrombopag dosing guidance for patients not meeting criteria for
sustained response

Platelet Level	Dose Guidance	
Patients with platelet < 30×10 ⁹ /L after 4 weeks of eltrombopag therapy at 75 mg/day	Discontinue eltrombopag, initiate second-line therapy, follow-up till week 52 and discontinue from study at Week 52	
Patients who relapse (platelet count < 30×10 ⁹ /L) during eltrombopag tapering off stage	Use previous dose level (i.e. one dose level higher) and continue treatment till Week 52 and discontinue from study at Week 52	

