9.1 Discontinuation

9.1.1 Discontinuation of study treatment

Early discontinuation of study treatment for a patient occurs when study treatment is stopped earlier than the protocol planned duration, and can be initiated by either the subject or the investigator.

The investigator must discontinue study treatment for a given subject if, he/she believes that continuation would negatively impact the subject's well-being.

Study treatment must be discontinued under the following circumstances:

- Patient/guardian decision
- Pregnancy
- Use of prohibited treatment as per recommendations in the prohibited treatment section
- Any situation in which study participation might result in a safety risk to the patient
- Any laboratory abnormalities that in the judgment of the investigator, taking into consideration the subject's overall status, prevents the subject from continuing participation in the study

If early discontinuation of study treatment occurs, the investigator should make a reasonable effort to understand the primary reason for the subject's premature discontinuation of study treatment and record this information.

Subjects who discontinue study treatment or who decide they do not wish to participate in the study further should NOT be considered withdrawn from the study UNLESS they withdraw

their consent (see withdraw of informed consent section,). Where possible, they should return for the assessments indicated in the assessment schedule. If they fail to return for these assessments for unknown reasons, every effort (e.g. telephone, e-mail, letter) should be made to contact the subject/pre-designated contact as specified in the lost to follow-up section. This contact should preferably be done according to the study visit schedule.

If the subject cannot or is unwilling to attend any visits, the site staff should maintain regular telephone contact with the subject, or with a person pre-designated by the subject. This telephone contact should preferably be done according to the study visit schedule.

After study treatment discontinuation, at a minimum, in abbreviated visits, the following data should be collected at clinic visits or via telephone/email contact:

- new / concomitant treatments
- AEs/SAEs

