12.4.2 Statistical model, hypothesis, and method of analysis

The analysis of the primary endpoint will be based on the following estimand:

The population will be the Full Analysis Set;

Variable of interest: The primary endpoint is the response rate in terms of sustained response off treatment at 52 weeks, in absence of bleeding or use of rescue therapy as defined above, i.e. a composite estimand.

Intervention effect: effect of eltrombopag in combination with a short course of high-dose dexamethasone versus 1-3 cycles of high-dose dexamethasone alone at 52 weeks, regardless of adherence to randomized treatment.

Summary measure: odds ratio

The statistical hypothesis to be rejected is that the rates of patients achieving sustained response at 52 weeks are equal in both treatment groups. The corresponding alternative hypothesis is that the rates are not equal under eltrombopag combined with a short course of high-dose dexamethasone, compared to 1-3 cycles of high-dose dexamethasone monotherapy.

Let p_A and p_B denote the proportions of patients achieving sustained response off treatment for the treatment groups:

A = eltrombopag combined with a short course of high-dose dexamethasone

B = 1-3 cycles of high-dose dexamethasone "standard"

The following hypotheses will be tested:

H₀: $(p_B / (1 - p_B)) / (p_A / (1 - p_A)) = OR_{B/A} = 1$

versus H_A : $(p_B / (1 - p_B)) / (p_A / (1 - p_A)) = OR_{B/A} \neq 1$

In other words:

 H_0 : The rate of patients achieving a sustained response off treatment at 52 weeks in the eltrombopag plus a short course of high-dose dexamethasone arm is equal to the respective rate in the 1-3 cycles high-dose dexamethasone monotherapy "standard" arm (corresponding to equal odds).

 H_A : The rate of patients achieving a sustained response off treatment at 52 weeks in the eltrombopag plus a short course of high-dose dexamethasone arm is higher than the respective rate in the 1-3 cycles of dexamethasone monotherapy "standard" arm.

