12.4.3 Handling of missing values/censoring/discontinuations

If patient's platelet assessment for evaluating the primary endpoint are missing, they will not be considered for sustained response off treatment. Patients dropping out early will be considered as early discontinuation or not evaluable, will be considered in the analysis set as non-responders. Thus, missing values are not expected for the primary analysis. Details will be specified in the respective SAP.

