#### 2.5.3 Handling of missing values/censoring/discontinuations

If patient's platelet assessment for evaluating the primary endpoint are missing, they will be assessed as non-responder. Patients dropping out early will be considered as early discontinuation or not evaluable, will be considered in the analysis set as non-responders. Thus, missing values are not expected for the primary analysis.

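### Protocol 6.5.3 takes patients who stop eltrombopag for an adverse event off the study, against 9.1.1 and the estimand; separately, two liver rules disagree on what follows a stop

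*Protocol*

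**What the plan says.** **Follow-up after stopping.** Protocol 6.5.3: "Patients who permanently discontinue eltrombopag for an AE or clinically significant laboratory value will be discontinued from the study", with a 30-day safety follow-up afterwards. Protocol 9.1.1 lists safety risk and laboratory abnormalities among the reasons to stop treatment. It then says that patients who stop "should NOT be considered withdrawn from the study UNLESS they withdraw" consent, and that they should come back for scheduled assessments where possible. It also sets a floor: "After study treatment discontinuation, at a minimum, in abbreviated visits, the following data should be collected at clinic visits or via telephone/email contact". That list holds new or concomitant treatments and adverse events, but no platelet count. For patients without response at 75 mg, Table 6-1 (Protocol 6.1) says: "Discontinue eltrombopag, initiate second-line therapy, follow-up till week 52 and discontinue from study at Week 52".

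**Endpoint and scoring.** Protocol 12.4.2 and SAP 2.5.2 define the Week 52 effect "regardless of adherence to randomized treatment". The failure components in Protocol 12.4.1 are a platelet count below 30 × 10⁹/L, bleeding of Grade II or higher, and rescue therapy. Stopping for an adverse event is not one of them. Early dropouts "will be considered in the analysis set as non-responders" (Protocol 12.4.3). SAP 2.5.3 says of patients with missing platelet data: "they will be assessed as non-responder".

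**What is still collected.** A patient who leaves early has an end-of-study visit with haematology and the WHO bleeding scale (Protocol 8, Table 8-1, and 9.2). Protocol 10.2.1 requires weekly platelet counts for four weeks after eltrombopag is stopped.

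**Liver rules.** For isolated ALT above 5 and up to 10 × ULN, Table 6-5 interrupts dosing and then resumes it at the same dose, or one level lower if recovery takes more than 14 days. Above 10 and up to 20 × ULN it interrupts and resumes one level lower. Protocol 6.5.3.1 lists ALT of at least 5 × ULN with normal baseline as a criterion on its own. It orders immediate discontinuation for those patients and is silent on restart.

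**The concern.** Sections 6.5.3 and 9.1.1 cover the same patients and cannot both be followed. If 6.5.3 is taken as the specific rule that prevails, it still conflicts with an estimand that disregards adherence. The plan would end response follow-up because of an adverse event on one drug, and then enter the missing outcome as failure.

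The contrast with Table 6-1 makes the clause hard to defend. Patients who stop for lack of efficacy are followed to Week 52 although second-line therapy has already made them non-responders. Patients who stop for an adverse event, whose outcome may still be open, are not. At stake is a downward distortion of the Arm A response rate that the report could not resolve afterwards.

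The liver point is one of conduct and safety: for the same isolated ALT value, two sections give the site different instructions.

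**Working it through.** **1. Who is affected.** The clause names eltrombopag only, and there is no matching rule for dexamethasone. Arm B patients receive eltrombopag only after fewer than 30 × 10⁹/L following three cycles, or after relapse (Table 6-2), so they have already failed the primary endpoint. Only Arm A outcomes are exposed. Protocol 8.4.5 also removes pregnant patients, but in both arms.

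**2. Follow-up lost.** Table 8-1 schedules platelet counts on Day 1 of Weeks 1 to 5, every two weeks from Week 7 to 33, and at Weeks 37, 41, 45, 49 and 53.
- Stop at Week 5: 14 + 5 = 19 scheduled counts remain. Two (Weeks 7 and 9) fall within the four weeks of weekly counts, so 17 lie beyond.
- Stop at Week 13: 10 + 5 = 15 remain. Two (Weeks 15 and 17) fall within the four weeks, so 13 lie beyond.

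The end-of-study visit adds one count early on and does not replace the later ones.

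**3. The plan's own figure.** Protocol 12.8.1 gives about 24% power for 30% versus 65% with about 24 patients (12 per arm). The continuity-corrected normal formula is Φ[(d − 1/n − 1.96·SE₀)/SE₁], with:
- d = 0.35 and n = 12
- SE₀ = √(2·0.475·0.525/12) = 0.204
- SE₁ = √((0.65·0.35 + 0.30·0.70)/12) = 0.191

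This gives Φ(−0.70) = 0.243. The figure reproduces and is not disputed. The same inputs are used below.

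**4. Size per affected patient.** Let p be the chance that a withdrawn Arm A patient would have been a responder if followed. The documents give no value, so p is assumed between 0 and 0.65. The expected loss in the Arm A rate is p/12.

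| p (assumed) | One patient | Two patients |
|---|---|---|
| 0 | 0 | 0 |
| 0.10 | 0.8 points | 1.7 points |
| 0.30 | 2.5 points | 5.0 points |
| 0.65 | 5.4 points | 10.8 points |

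The number affected is also an assumption and may be zero. For scale, the 95% half-width of the rate difference is 1.96 × 0.191 = 0.374, or about 37 points.

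**5. Does the SAP recover it?** Only in part. SAP 2.3.1 tabulates reasons for discontinuation. SAP 2.5.4 has one non-response class for data missing until Week 53, which pools all causes. Of its two sensitivity analyses, one needs platelet counts through Week 53 and the other keeps only completers. Multiple imputation is an option in Protocol 12.4.4 but is not in the SAP list.

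**6. Liver rules side by side, normal baseline, isolated ALT.**

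| ALT (× ULN) | Table 6-5 | 6.5.3.1 |
|---|---|---|
| >5 to 10 | interrupt; resume at same dose, or lower if slow | discontinue at once; restart not addressed |
| >10 to 20 | interrupt; resume one level lower | discontinue at once; restart not addressed |
| >20 | discontinue | discontinue |

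Protocol 6.5.2 and 10.2.1 point to Table 6-5 but do not cancel 6.5.3.1.

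**The case against.** Most of the case on the other side concerns size, and much of it stands.

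- **These patients are not simply unobserved.** A reader might infer that nothing is known after the stop. The end-of-study visit and the four weekly counts say otherwise. Protocol 4.5.1 adds that after stopping, "platelet counts return to baseline levels within 2 weeks in the majority of patients", so most relapses would fall inside that window. What is lost is later follow-up of the minority who hold their counts.
- **Many would fail anyway.** Protocol 10.2.1 recommends restarting ITP treatment after a stop, and Protocol 6.2.3 scores ITP-directed therapy after discontinuation as non-response.
- **Responder status is unsettled.** Protocol 6.1.4 ties response follow-up to stopping as the design foresees, and SAP 2.5.1 and 5.5.1.1 leave response to data review. If patients who stop before the taper are classed as non-responders in any case, the clause changes little.
- **The scoring rule is prespecified and conservative.** It can only work against the sponsor's drug, in an analysis that Amendment 3 made descriptive. This is true, but it does not reconcile 6.5.3 with 9.1.1 or with the estimand.
- **The 9.1.1 minimum list also covers telephone contact**, where no platelet count can be drawn, and bleeding is already recorded as an adverse event (Protocol 8.3.2). The gap matters only for abbreviated visits held in clinic.

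On the liver rules, 6.5.3.1 does not use the word permanent and follows a medical review for cholestasis. It can be read as stopping pending work-up. That leaves an ambiguity on restart, and the text should settle it.

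**Conclusion.** The plan is wrong as written on both points. The statistical point is minor. Section 6.5.3 contradicts 9.1.1 and does not serve the estimand. Its effect on the primary endpoint is confined to Arm A and runs against eltrombopag. The size is unknown and possibly zero: 0 to 5.4 points per affected patient, assuming 12 per arm and a response chance of 0 to 0.65, with Protocol 4.5.1, 10.2.1 and 6.2.3 pointing to the low end.

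A reader might infer a demonstrated bias. The documents do not support that, because they give neither the number of adverse-event stops nor the outcome those patients would have had. No false claim of benefit can follow.

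The liver conflict is a patient-safety correction in its own right. Three stronger readings are not supported:
- **That 6.5.3.1 certainly ends treatment for good.** It is silent on restart.
- **That Protocol 8.4.2.2 is a conflicting third rule.** It largely repeats the Table 6-5 row for ALT above 3 and up to 5 × ULN, with raised direct bilirubin as the main addition.
- **That the combined ALT and bilirubin rules for raised baseline can be ranked by strictness.** Their ALT limits do differ: above 3 × baseline or 5 × ULN, whichever is lower, in Table 6-5; above 2 × baseline and 3 × ULN, or above 8 × ULN, in 6.5.3.1. But both texts require stopping, and the bilirubin limit of Table 6-5 is cut off in the available text, so the full rules cannot be compared.

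**What to change.** **Follow-up.** Strike the study-withdrawal clause in 6.5.3 so that 9.1.1 governs. Patients who stop for an adverse event then have scheduled platelet, bleeding and rescue assessments to Week 53 Day 1. Require a platelet count at any abbreviated visit held in clinic. The cost is a short written amendment, a site letter, and scheduled counts for the patients concerned.

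**If patients have already been withdrawn.** Report the number per arm withdrawn under 6.5.3 and add one sensitivity analysis. To be a true upper bound, it must count as responders all such patients with no observed platelet count below 30 × 10⁹/L, no Grade II or higher bleeding, and no rescue or other ITP-directed therapy after stopping, including those with no count after the stop. The primary scoring is the lower bound. If a post-stop count is required, call the result a sensitivity analysis and not a bound. Some of those counted would have relapsed later, so the label matters. SAP 3.0 was agreed just before database lock. After lock this reporting is all that remains possible, and it needs no new data.

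**Liver rules, separately.** Give one instruction in Table 6-5 and 6.5.3.1 for isolated ALT above 5 and up to 20 × ULN with normal baseline, and say whether restart is allowed. Align the ALT limits for combined elevation with raised baseline. The clinical choice is the sponsor's, and the cost is an edit to two places in the protocol.
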